#### 9.4.3 ANALYSIS OF PRIMARY EFFECTIVENESS ENDPOINTS

The statistical analyses described in ISO 11979-7, ISO 11979-9, and ANSI Z80.12 will be performed unless otherwise specified in the statistical analysis plan.

The co-primary effectiveness endpoints are:

- Photopic monocular logMAR best corrected distance visual acuity (BCDVA) in first operative eyes at Month 6 (Visit 4)
- Photopic monocular logMAR distance corrected near visual acuity (DCNVA) in first operative eyes at Month 6 (Visit 4)

Primary effectiveness endpoint analyses will be based on the All-implanted Analysis Set. Imputation of missing data will be performed utilizing multiple imputation techniques under assumptions of missing at random and missing not at random following the primary strategy presented in Section 9.4.2. As sensitivity analyses, the primary effectiveness analyses will be repeated using the secondary multiple imputation strategies presented in Section 9.4.2, as well as on the ITT and Best Case Sets using the primary multiple imputation strategy only. If the results of the ITT or Best Case Set robustness analyses materially differ from the primary analyses on the All-implanted Analysis Set then the results of investigations into the cause of such differences will be presented.

Photopic monocular BCDVA in first operative eyes at Postoperative Month 6 (Visit 4) will be primarily summarized using continuous summary statistics by treatment group. The treatment effect [mean Test group IOL visual acuity (VA) minus mean Control group IOL VA] in logMAR units will be presented in addition to a two-sided 90% t-distribution confidence interval around the difference. If the upper confidence limit is less than 0.1, then  $H_{01e}$  will be rejected in favor of  $H_{11e}$  and the FINEVISION HP IOL will be considered to be statistically non-inferior to the AcrySof SN60AT [REDACTED] IOL in BCDVA.

Photopic monocular DCNVA in first operative eyes at Postoperative Month 6 (Visit 4) will be summarized using continuous summary statistics in logMAR units by treatment group. The FINEVISION HP IOL will be compared to the AcrySof SN60AT [REDACTED] IOL using a two-sample t-test with a two-sided alpha of 0.05. If the two-sided p-value < 0.05 in favor of FINEVISION HP IOL for DCNVA, then the FINEVISION HP IOL will be considered to be statistically superior to the AcrySof SN60AT [REDACTED] IOL in DCNVA.

The study will be considered a success only if both primary effectiveness endpoints are met.

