## 7.3 Best Case Set

The Best Case Set will include subjects with all of the following characteristics:

- No major protocol deviations potentially affecting any of the primary effectiveness endpoints (BCDVA, DCNVA). Major protocol deviations that may potentially affect the primary effectiveness endpoints include, but are not limited to:
  - Inclusion of ineligible subjects
  - Implantation of incorrect IOL
  - Missed assessments for effectiveness endpoints at Month 6 (Visit 4)
  - Receipt of medication likely to interfere with visual performance at Month 6 (Visit 4)

- At least one eye implanted with a study lens
- No clinically significant preoperative ocular pathology in the first operative eye, including any of the following present prior to the Operative Visit:
  - Pseudoexfoliation of lens capsule
  - Glaucoma
  - Uveitis
  - Retinal detachment
  - Diabetic retinopathy
  - Macular degeneration
  - Amblyopia
  - Other preoperative pathologies that are likely to affect central acuity
- No macular degeneration detected at any time in the first operative eye
- No previous surgery for the correction of refractive errors in the first operative eye

Summaries and analyses based on the Best Case Set will analyze subjects as treated.

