  class trt;
  var base aval_v3 aval_v4 aval_v5;
  MONOTONE REG(aval_v4 = aval_v3);
  MONOTONE REG(aval_v5 = aval_v4 aval_v3);
  MNAR MODEL(aval_v4 aval_v5 / MODELOBS=(trt= "2"));
run;

```

Thirty complete datasets will be generated from the above code.

A two-sample t-test will be performed for each imputed dataset and the results of the t-tests will be pooled using PROC MIANALYZE. SAS® code similar to the code below will be used to perform the primary analysis for each imputed dataset and then combine inferences across the imputed datasets:

```

proc sort data = mi;
  by _imputation_;
run;

ods output statistics = stat1(where = (Method ne
"Satterthwaite"));
proc ttest data = mi alpha = α
  by _imputation_;
  class trt;
  var aval_v4;
run;

proc sort data = stat1;
  by class _imputation_;
run;

ods output ParameterEstimates = pes;
proc mianalyze data = stat1 alpha = &alpha theta0 = &theta0;
  modeleffects Mean;
  stderr STDERR;
  by class;
run;

```

where

- $\&\alpha$ lpha = the significance level; 0.10 for BCDVA and 0.05 for DCNVA

- $\theta_0$  = the assumed difference in population means under the null hypothesis, 0.10 for BCDVA and 0 for DCNVA

After pooling the statistical analyses across the imputation datasets, the output dataset resulting from PROC MIANALYZE will contain means and standard errors for each treatment group and for the difference in treatment groups (test minus control), a CI for the treatment group difference (90% CI for BCDVA and 95% CI for DCNVA), and a two-sided p-value testing for whether the difference in treatment group means equals 0. These statistics from PROC MIANALYZE will comprise the primary effectiveness analyses for the primary effectiveness endpoints. If the upper confidence limit of the 90% confidence interval for the difference in treatment group means for BCDVA at Month 6 (Visit 4) is less than 0.1, then  $H_{0e}$  will be rejected in favor of  $H_{1e}$ , and the FINEVISION HP IOL will be considered to be statistically non-inferior to the AcrySof® SN60AT [REDACTED] IOL in BCDVA. If the two-sided p-value < 0.05 in favor of FINEVISION HP IOL for DCNVA at Month 6 (Visit 4), then the FINEVISION HP IOL will be considered to be statistically superior to the AcrySof® SN60AT [REDACTED] IOL in DCNVA.

The study will be considered a success only if both primary effectiveness endpoints are met.

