### 13.1.4 SUBGROUP ANALYSES

As subgroup analyses, the primary analyses of photopic monocular BCDVA and DCNVA will be repeated for first operative eyes from the AAS at Month 6 (Visit 4) for the following photopic pupil size subgroups: small (< 2.5 mm), medium (2.5 to  $\leq$  4mm), and large (> 4 mm). Photopic pupil size at Month 6 (Visit 4) will be used to create the pupil size subgroups.

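### The SAP pools its t-tests in PROC MIANALYZE without complete-data degrees of freedom, so intervals and p-values in the pupil-size subgroups are anti-conservative if a subgroup is small

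*SAP*

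**What the plan says.** SAP 13.1 sets out the analysis of each imputed dataset and the pooling: "A two-sample t-test will be performed for each imputed dataset and the results of the t-tests will be pooled using PROC MIANALYZE". The number of imputations is 30 ("Thirty complete datasets will be generated from the above code"). The pooling statement is "proc mianalyze data = stat1 alpha = &alpha theta0 = &theta0;". It receives a mean and a standard error for each arm and for the difference, processed by class, and nothing that carries the t-test's degrees of freedom. The alpha value is "the significance level; 0.10 for BCDVA and 0.05 for DCNVA", which gives a 90% and a 95% interval respectively. The code is introduced as illustrative.

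Protocol 9.4.3 describes the primary BCDVA comparison as a "two-sided 90% t-distribution confidence interval around the difference", and the DCNVA comparison as a two-sample t-test.

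SAP 13.1.4 repeats the primary BCDVA and DCNVA analyses within photopic pupil-size groups (below 2.5 mm, 2.5 to 4 mm, above 4 mm) defined by the Month 6 measurement. SAP 13.2 does the same for DCIVA. Neither section gives an expected count, a minimum subgroup size or a small-sample correction. SAP 7.3 treats a missed Month 6 effectiveness assessment as a major deviation that removes a subject from the Best Case Set.

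**The concern.** A t-test on n eyes takes its critical value from a t distribution with n − 2 degrees of freedom. When several t-tests are pooled after imputation, that figure has to be passed to the pooling step. Otherwise the complete-data degrees of freedom are taken as infinite. The pooled value then depends only on the number of imputations and on the ratio of between- to within-imputation variance.

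That ratio is small where little Visit 4 acuity is missing. This is the likely situation in the pupil subgroups, because membership requires a Visit 4 measurement. It also applies in the Best Case Set.

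At stake is the accuracy of the intervals and p-values in any small pupil subgroup. The error always runs one way: intervals too narrow and p-values too small. The SAP already handles this properly elsewhere. The by-site code in SAP 13.1.5 takes its p-values from a t distribution with the model's degrees of freedom.

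**Working it through.** **Inputs.** m = 30 imputations, the pooling call and the alpha levels (SAP 13.1). 300 and 150 eyes, SD 0.10 with margin 0.10 for BCDVA, SD 0.14 with difference −0.10 for DCNVA (SAP 5.1). 501 subjects with 10% loss (SAP 5). Subgroup sizes are not in the documents and are assumed below.

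**1. The plan's own figure.** The standard error for BCDVA is 0.10 × √(1/300 + 1/150) = 0.010, so the margin is 10 standard errors away and power is about 100%. For DCNVA it is 0.14 × √(1/300 + 1/150) = 0.014. The difference is 7.14 standard errors, and 7.14 − 1.96 = 5.18, so power is above 99.9999%. The stated figure of more than 99% is reproduced. A change of a few tenths of a percent in interval width cannot matter at this power.

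**2. Pooled degrees of freedom without EDF=.** ν = (m − 1)(1 + 1/r)², with r = (1 + 1/m)B/W. Taking B/W = f/(1 − f) for a missing fraction f (an upper bound, with no help from earlier visits):

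| f | r | ν | 90% critical value | 95% critical value |
|---|---|---|---|---|
| 10% | 0.1148 | 2,734 | 1.6454 | 1.9608 |
| 5% | 0.0544 | 10,900 | 1.6450 | 1.9602 |
| 2% | 0.0211 | 67,989 | 1.6449 | 1.9600 |

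The number of eyes does not enter. The normal values are 1.6449 and 1.9600, so a subgroup of 10 eyes would be judged against what is numerically the normal distribution.

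**3. Full set, with complete-data degrees of freedom supplied.** The adjusted value is 1/(1/ν + 1/ν_obs), where ν_obs = [(ν_c + 1)/(ν_c + 3)] × ν_c × (1 − γ), ν_c = n − 2 and γ = r/(1 + r). At n = 501 and 10% missing it is 383, with critical values 1.6488 and 1.9662. The 90%/95% intervals without EDF= are too narrow by 0.21%/0.27%. At n = 450 the shortfall is 0.23%/0.30%.

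**4. Subgroups, no missing Visit 4 values.** Shortfall = 1 − z/t(n − 2). Actual alpha = 2 × P(t(n − 2) > 1.960). Here n is the total over both arms.

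| Assumed n | t, 90% | t, 95% | 90% interval too narrow by | 95% interval too narrow by | Actual two-sided alpha at nominal 0.05 |
|---|---|---|---|---|---|
| 12 | 1.8125 | 2.2281 | 9% | 12% | 0.078 |
| 15 | 1.7709 | 2.1604 | 7% | 9% | 0.072 |
| 20 | 1.7341 | 2.1009 | 5% | 7% | 0.066 |
| 30 | 1.7011 | 2.0484 | 3% | 4% | 0.060 |
| 60 | 1.6716 | 2.0017 | 1.6% | 2.1% | 0.055 |
| 100 | 1.6606 | 1.9845 | about 1% | 1.2% | 0.053 |

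The 90% column applies to BCDVA and the 95% column to DCNVA and DCIVA.

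**5. A little missing data makes it slightly worse.** At n = 12 and 2% missing, the adjusted degrees of freedom are 8.3 and the critical values 1.8513 and 2.2922. The shortfalls are then 1 − 1.6449/1.8513 = 11% and 1 − 1.9600/2.2922 = 14%.

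**6. Simulation of the 90% interval** (2% missing, 4,000 repetitions, Monte Carlo standard error about 0.5 points). Coverage without and with EDF= was 87.3% and 90.4% at 8 versus 4 eyes, 89.2% and 90.7% at 14 versus 6, and 88.8% and 89.7% at 20 versus 10. The direction matches the formula in each case.

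**The case against.** The case for leaving this alone is substantial.

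- **No decision depends on it.** Study success rests on the two primary endpoints, the hierarchy covers only primary and secondary tests, and the subgroups carry no success criterion. This stands.
- **Subgroup sizes are unknown.** Nothing in the documents says that either outer group will be small, and the effect is about 2% or less from 60 eyes upwards. This stands. The 0.5 mm gauge in SAP 16.8 means that the lowest group needs a reading of 2.0 mm or less, which makes a small group plausible but does not establish one.
- **The code is only illustrative.** The final program could add the option. That is true, but nothing in the SAP says that it will.
- **Formally the reference is still a t distribution.** With thousands of degrees of freedom, the distinction has no numerical content.

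Two stronger readings are tempting, and the documents do not support them. A reader might infer that the subgroup intervals contradict Protocol 9.4.3. That section specifies a t-based interval only for the primary BCDVA comparison in the All-Implanted Analysis Set, where the effect is about 0.2%. For pupil size, Protocol 9.4.10 plans only summary statistics, and SAP 1 states that its methods supersede the protocol's.

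A reader might also infer that the affected analyses were added at FDA's request. SAP 19, item 5, attributes the three-way split to the sponsor. What it lists as added in response to FDA comments are analyses of the secondary safety endpoints and adverse events, which do not use this pooling code. Effectiveness summaries by pupil size were already in the protocol.

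**Conclusion.** The point holds as a minor matter of reporting accuracy. The pooling step as written discards the t-test's degrees of freedom, and the SAP repeats it in subgroups of unspecified size. The co-primary and secondary results in the full set are unaffected, with a shortfall of 0.2% to 0.3%. The Best Case Set is open to the same omission, but nothing suggests that it will be small.

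In the pupil subgroups the error is anti-conservative. It ranges from about 1% of interval width at 100 eyes to 9% (90% interval) or 12% (95% interval) at 12 eyes. These figures rest on assumed subgroup totals and on no missing Visit 4 acuity within the subgroup. Because the SAP goes beyond the protocol's descriptive plan and presents inferential results by pupil size, it should use the correct reference distribution for them.

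**What to change.** In SAP 13.1, and by reference in 13.1.4 and 13.2:

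- Supply EDF = n_test + n_control − 2 to PROC MIANALYZE for the difference row, set separately for each subgroup and analysis set. The call runs by class, so the arm rows need separate handling: use n − 1 for any single-arm row whose interval is reported.
- Where no Visit 4 value is imputed, so that the between-imputation variance is zero, report the ordinary t-test interval and p-value. Apply this to the pupil subgroups as well as the Best Case Set.

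The cost is a short change to the program and a sentence or two in the SAP. It needs no new data and leaves the full-set conclusions as they are. Intervals in small subgroups become wider, as they should.

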### 13.1.1 SENSITIVITY ANALYSIS I

The sensitivity analysis described in this section will only be performed for BCDVA in first operative eyes at Month 6 (Visit 4) for the AAS. The handling of intercurrent events will be updated as follows:

1. Withdrawal due to physician decision: missing data assumed to be MNAR. Treatment-based multiple imputations, *using the worst half of the subjects who have data within the same treatment group*, will be completed for non-inferiority hypotheses. [hypothetical strategy]
2. Missing data without withdrawal or withdrawal due to reasons other than due to physician decision: missing data assumed to be MAR. Treatment-based multiple imputations will be completed. [hypothetical strategy]

SAS® code similar to the code below will be used to identify the worst half of subjects for BCDVA by treatment group at Month 6 (Visit 4):

```

proc sort data = indata;
  by trt;
run;

proc means data = indata noprint;
  var aval_v4;
  by trt;
  output out = v4_median(drop = _TYPE_ _FREQ_) median =
median_v4;
run;

data indata(drop = median_v4);
  merge indata v4_median;
  by trt;

```

```

  if aval_v4 >= median_v4 then worse_median_flg = "Y";
  else worse_median_flg = "N";
run;

```

If a subject has no observed BCDVA data at any of the scheduled visits, BCDVA will be imputed at the earliest scheduled visit as described in [Section 13.1](#). Non-monotone missing data will first be imputed using treatment-based MCMC methodology as described in [Section 13.1](#).

After imputation of non-monotone missing data, the BCDVA data will be partitioned into a dataset containing missing data due to withdrawal due to physician decision and a data set containing the remaining BCDVA data, including missing data due to any other reason:

```

/* Split mcmc into cases where missing is due to withdrawal due
to physician decision or other */
data mcmc1;
  set mcmc (where = (DSDECOD ne "Physician Decision"));
run;

data mcmc2;
  set mcmc (where = (DSDECOD = "Physician Decision"));
run;

```

where

- DSDECOD = reason for discontinuation.

The monotone missing data not due to withdrawal due to physician decision will be imputed using treatment-based regression methodology using SAS® code similar to the code below:

```

/* Impute missing data not due to Physician Decision using
treatment-based regression methodology */
proc sort data = mcmc1;
  by trt _imputation_;
run;

proc mi data = mcmc1 out = mil nimpute = 1 seed = 891568 round =
0.02;
  by trt _Imputation_;
  var base aval_v2 aval_v3 aval_v4 aval_v5;
  monotone reg(aval_v2 = base);
  monotone reg(aval_v3 = aval_v2 base);
  monotone reg(aval_v4 = aval_v3 aval_v2 base);
  monotone reg(aval_v5 = aval_v4 aval_v3 aval_v2 base);
run;

```

The resulting imputed data will then be combined with the missing data due to withdrawal due to physician decision. If there is any missing data due to withdrawal due to physician decision, it will be imputed using treatment-based regression methodology, using the worst half of the subjects who have data within the same treatment group, for BCDVA using SAS® code similar to the code below:

```

/* Impute missing data due to Physician Decision
median subjects using regression methodology */
data mcmc2;
  set mil mcmc2;
run;

proc sort data = mcmc2;
  by trt _imputation_;
run;

proc mi data = mcmc2 out = mi2 nimpute = 1 seed = 891568 round =
0.02;
  by trt _imputation_;
  class worse_median_fl;
  var base aval_v2 aval_v3 aval_v4 aval_v5;
  MONOTONE REG(aval_v2 = base);
  MONOTONE REG(aval_v3 = aval_v2 base);
  MONOTONE REG(aval_v4 = aval_v3 aval_v2 base);
  MONOTONE REG(aval_v5 = aval_v4 aval_v3 aval_v2 base);
  MNAR MODEL(aval_v2 aval_v3 aval_v4 aval_v5 /
  MODELOBS=(worse_median_fl = "Y"));
run;

```

where

- worse\_median\_fl = Y if the BCDVA at Month 6 (Visit 4) is greater than or equal to than the treatment group median

The imputed datasets will be analyzed and pooled using the same methodology and summarized similarly as the primary analyses.

### 13.1.2 SENSITIVITY ANALYSIS II

The primary analyses will be repeated for the ITT Set using the primary multiple imputation strategy as specified in [Section 13.1](#) for both primary effectiveness endpoints.

For subjects from the ITT Set who are not implanted with an IOL, the first operative eye will be imputed using the same criteria for selecting the first operative eye as described in [Section 8.1](#).

### 13.1.3 SENSITIVITY ANALYSIS III

The primary analyses will be repeated for the Best Case Set using the primary multiple imputation strategy as specified in [Section 13.1](#) for both primary effectiveness endpoints.

### 13.1.4 SUBGROUP ANALYSES

As subgroup analyses, the primary analyses of photopic monocular BCDVA and DCNVA will be repeated for first operative eyes from the AAS at Month 6 (Visit 4) for the following photopic pupil size subgroups: small (< 2.5 mm), medium (2.5 to  $\leq$  4mm), and large (> 4 mm). Photopic pupil size at Month 6 (Visit 4) will be used to create the pupil size subgroups.

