#### 9.4.10 SUB-GROUP ANALYSES

Summary statistics for primary and secondary effectiveness endpoints, as well as primary safety endpoints, will be presented by postoperative photopic pupil size ( $\leq 4\text{mm}$ ;  $> 4\text{mm}$ ).

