### **8.4 Data Analysis Conventions**

All data analysis will be performed by [REDACTED]. Statistical programming and analyses will be performed using SAS® version 9.4 or higher. Output will be provided in rich text format (RTF) for tables and portable document format (PDF) for tables, listings, and figures using landscape orientation.

Summaries for continuous and ordinal variables will include the number of observations (n), arithmetic mean, SD, median, minimum, and maximum. Minima and maxima will be reported with the same precision as the raw values; means and medians will be presented to one additional decimal place than reported in the raw values. Standard deviations will be presented to two additional decimal places than reported in the raw values. Summaries for discrete variables will include counts and percentages. All percentages will be rounded to one decimal place (i.e., XX.X%). Differences between test and control treatment groups will be calculated as test minus control and change from baseline will be calculated as follow-up visit minus baseline.

All statistical tests will be one-sided with a significance level of 0.05 ( $\alpha = 0.05$ ), except for the two superiority tests of DCIVA and DCNVA which will be two-sided with a significance level of 0.05. Correspondingly, confidence intervals (CI) for differences between treatment groups will be two-sided at 90% or 95% confidence. All p-values will be rounded to 4 decimal places; p-values less than 0.0001 will be presented as “<0.0001”; p-values greater than 0.9999 will be presented as “>0.9999.”

Unless otherwise specified, summaries will be presented by treatment group and, where appropriate, visit. Listings will be presented by subject number, treatment group, visit/time point, and parameter as applicable.

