### 13.2 Secondary Analyses

The secondary effectiveness endpoint is:

- Photopic monocular logMAR intermediate (66 cm) visual acuity with distance correction (DCIVA) in first operative eyes at Month 6 (Visit 4)

The secondary effectiveness endpoint will be based on the AAS. The primary analysis for DCNVA will be repeated for photopic DCIVA (66 cm) in first operative eyes at Month 6 (Visit 4). If the two-sided p-value < 0.05 in favor of FINEVISION HP IOL for DCIVA, then the FINEVISION HP IOL will be considered to be statistically superior to the AcrySof® SN60AT [REDACTED] IOL in DCIVA.

Inference will be conducted for the secondary effectiveness analysis only if all primary effectiveness endpoints are met.

The sensitivity analyses for DCNVA will also be repeated for photopic DCIVA (66 cm) in first operative eyes at Month 6 (Visit 4).

Subgroup and poolability analyses of photopic monocular DCIVA (66 cm) in first operative eyes from the AAS at Month 6 (Visit 4) will be performed similarly as those for DCNVA.

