## 19. Changes from Protocol-Stated Analyses

The SAP includes the following changes from the protocol-stated analyses:

1. [REDACTED]

[REDACTED]

[REDACTED]

[REDACTED]

3. The reason for missing data “withdrawal due to investigator’s request” from the protocol has been updated to “withdrawal due to physician decision” in the SAP to match the corresponding reason for discontinuation term from the end of study eCRF.
4. Summaries of AEs by investigator from the protocol have been updated to summaries of AEs by site in the SAP.
5. Pupil size subgroups for sub-group analyses of primary and secondary effectiveness and safety endpoints have been updated from ( $\leq 4\text{mm}$ ,  $> 4\text{mm}$ ) in the protocol to small ( $< 2.5\text{ mm}$ ), medium ( $2.5\text{ to } \leq 4\text{mm}$ ), and large ( $> 4\text{ mm}$ ) in the SAP per sponsor request. Pupil size subgroup analyses of the secondary safety endpoints and overall adverse events were added to the SAP to address FDA comments requesting safety and effectiveness subgroup analyses by pupil size.

[figure not shown]

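### Repeating the effectiveness tests within pupil-size groups (SAP 13.1.4 and 13.2) cannot show whether the lens effect depends on pupil size, and no treatment-by-pupil interaction is planned

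*SAP*

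**What the plan says.** Protocol 9.4.10 plans description only, in two groups split at 4 mm: "Summary statistics for primary and secondary effectiveness endpoints, as well as primary safety endpoints, will be presented by postoperative photopic pupil size".

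The SAP, which by its introduction overrides the protocol's methods, goes further. Section 13.1.4 reads: "As subgroup analyses, the primary analyses of photopic monocular BCDVA and DCNVA will be repeated for first operative eyes". There are three groups (small, medium, large), and "Photopic pupil size at Month 6 (Visit 4) will be used to create the pupil size subgroups". Section 13.2 extends this to the secondary endpoint: "Subgroup and poolability analyses of photopic monocular DCIVA (66 cm) in first operative eyes from the AAS" at Month 6 "will be performed similarly as those for DCNVA".

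The analysis being repeated is multiple imputation followed by inference: "A two-sample t-test will be performed for each imputed dataset and the results of the t-tests will be pooled using PROC MIANALYZE". Its output is a treatment difference, a 90% or 95% confidence interval and a p-value. Section 13.1 then gives the overall rules for declaring non-inferiority in BCDVA and superiority in DCNVA.

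On levels, SAP 8.4 says "All statistical tests will be one-sided with a significance level of 0.05", with an exception that makes the two superiority tests two-sided at 0.05. SAP 8.5 covers the overall primary and secondary tests, and both 8.5 and 13.2 make secondary inference conditional on success of the primaries. SAP 13.1.5 fits a site-by-treatment interaction, judged at 0.15. No legible passage fits one for pupil size.

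SAP 19 item 5 records the new cut-points. It says that subgroup analyses of the secondary safety endpoints and adverse events were added "to address FDA comments requesting safety and effectiveness subgroup analyses by pupil size". In its legible text it does not mention the move from summaries to repeated tests.

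**The concern.** The reason to look at pupil size is to learn whether the lens performs differently in small, medium and large pupils. Three separate p-values per endpoint do not answer that. One group can reach significance and another miss it although the true effect is the same in both, because the groups differ in size or by chance. Conversely, all three can be significant while the effects differ materially. The comparison that addresses the question is between the group-specific treatment differences, and the SAP plans no such comparison.

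There is also a risk in reporting. Section 13.1.4 invokes the primary analyses without saying whether their decision rules come too. A report could then state non-inferiority or superiority in a particular pupil group, although no error rate was set for such statements.

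**Working it through.** **Inputs from the documents.** 300 test and 150 control eyes. BCDVA: SD 0.10, margin 0.10, true difference 0, one-sided 0.05. DCNVA and DCIVA: difference -0.10, SD 0.14, two-sided 0.05 (protocol 9.2; SAP 5). Three pupil groups (SAP 13.1.4). The documents give no group sizes, so every share below is an assumption.

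**1. The plan's own power.** The factor sqrt(1/300 + 1/150) is 0.10.
- BCDVA: SE = 0.10 × 0.10 = 0.010, and 0.10/0.010 - 1.645 = 8.36.
- DCNVA and DCIVA: SE = 0.14 × 0.10 = 0.014, and 0.10/0.014 - 1.96 = 5.18.

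Both give power above 99%, as stated.

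**2. Count.** 3 endpoints × 3 groups = 9 analyses. Three are DCIVA and fall under the secondary gate, which leaves 9 - 3 = 6 with no gate.

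**3. What group size alone does.** Noncentral-t power in one group, with the planning effect unchanged:

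| Assumed share of 450 eyes | Test + control | BCDVA non-inferiority | DCNVA or DCIVA superiority |
|---|---|---|---|
| 5% | 15 + 8 | 71% | 34% |
| 10% | 30 + 15 | 93% | 60% |
| 20% | 60 + 30 | 99.7% | 89% |
| 33% | 99 + 50 | >99.9% | 98% |

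Now take small/medium/large shares of 5/65/30%, 10/60/30% or equal thirds, with a true difference of -0.10 in every group. The chance that all three groups reach significance on one superiority endpoint is 32%, 58% or 95% (computed with unrounded group sizes). A mixed pattern under a constant effect therefore has probability of about 68%, 42% or 5%.

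**4. Error rates if the 13.1 rules were carried into the groups.** The groups contain different subjects and are treated as independent.
- BCDVA, every group exactly at the margin: 1 - 0.95³ = 14.3%.
- DCNVA, no effect in any group, favourable direction only: 1 - 0.975³ = 7.3%.
- The six ungated analyses, endpoints uncorrelated: 1 - 0.95³ × 0.975³ = 1 - 0.8574 × 0.9269 = 20.5%. With endpoint correlation 1 this falls to 14.3%. In simulation it is 19.0% at correlation 0.5 and 16.7% at 0.8. The correlation is an assumption.

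**5. What an interaction test could detect.** Suppose the small group, with share s, differs from the other two by δ. The 2-df F test has noncentrality δ² × s(1 - s) × 100/SD² and 450 - 6 = 444 denominator df. With δ = 0.10 and SD 0.14, this is 51.02 × s(1 - s).

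| Share of small group | Noncentrality | Power at 0.05 | Power at 0.15 |
|---|---|---|---|
| 5% | 2.42 | 27% | 47% |
| 10% | 4.59 | 47% | 67% |
| 33% | 11.34 | 86% | 95% |

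For δ = 0.05 at the same SD, power at 0.05 is 10%, 15% and 30%. The interaction test asks the right question, but unless the groups are of similar size it may often miss a real difference.

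**The case against.** The best defence is that 13.1.4 re-uses a method and makes no claim. The section states no subgroup hypothesis or success rule, and the formal hypotheses in SAP 3.5 concern the overall comparison. Sections 13.1.2 and 13.1.3 use the same language of repetition for sensitivity analyses, where nobody would read new claims into it. SAP 8.4 speaks of two superiority tests, which suggests that subgroup repeats are not counted as tests. Study success depends only on the two overall co-primaries. The repeated analysis already yields a difference and a confidence interval in each group. The error rates in step 4 need every group to sit at its null boundary, whereas the design assumes differences of 0 and -0.10; under those assumptions no favourable subgroup result would be false. An interaction test may also be weak.

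Most of this stands, and it limits the point. A reader might infer that the SAP licenses nine ungated confirmatory subgroup verdicts. The documents do not support that: the DCIVA repeats are gated, no subgroup decision rule is written, and the step 4 rates are conditional on a reading that the text leaves open. A reader might also infer from SAP 19 that the change was left undisclosed. That cannot be settled, because earlier items in that list and SAP 17 and 18 are blacked out, and the regulator's comments are not visible.

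The defence does not supply a test of whether the effect varies with pupil size. Low interaction power is a reason to report it with estimates and intervals, not a reason to rely on separate p-values.

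**Conclusion.** The point holds as a gap in analysis and reporting. The SAP replaces the protocol's pupil-size summaries with nine repeated inferential analyses, six of them ungated, and none addresses whether the lens effect depends on pupil size. With an assumed small-pupil share of 5% to 10%, superiority power in that group is 34% to 60% even if the effect is identical everywhere, so a missed result there would say little about pupil size.

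The false-positive figures (14.3%, 7.3%, and 14.3% to 20.5%) apply only if the 13.1 decision rules are taken to carry over and every relevant null is true at its boundary. The overall primary conclusion, its type I error, the sample size and the study success rule are unaffected. This is a low-severity, low-cost improvement. Absence of an exploratory label and of a pupil interaction is judged on the legible text.

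**What to change.** In SAP 13.1.4, and in 13.2 for DCIVA:

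- Present treatment differences by pupil group with nominal confidence intervals, labelled exploratory, and state that no non-inferiority or superiority conclusion will be drawn within a group.
- Add one linear model per endpoint with treatment, pupil group and their interaction, on the pattern of the site model in 13.1.5, and state in advance the level at which the interaction will be flagged.
- State that a non-significant interaction does not show consistency, because power may be low, and that the reading rests on the estimates and intervals.
- Record in SAP 19 the change from the protocol's summary statistics.

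The model needs one set of groups. SAP 16.8 lists cut-points for the subgroup analyses that differ from those in 13.1.4, so the two sections should be reconciled in the same edit.

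The cost is SAP wording and one extra model per endpoint on data already collected. The limits are modest interaction power and the loss of any non-inferiority or superiority statement for a single pupil group.
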